#### 8.2.1 Premature Discontinuation of Study Drug

Data collected will be used regardless of premature discontinuation of study drug.

#### 8.2.2 UC-Related Corticosteroids

[figure not shown]
The UC-related corticosteroids intercurrent event is defined as follows.

- subjects not on UC-related corticosteroids (systemic or locally acting corticosteroids for UC) at Baseline who initiated UC-related corticosteroids during the Induction Study;
- subjects on UC-related systemic corticosteroids at Baseline who have dosages increased to greater than the prednisone equivalent dose of corticosteroid taken at Baseline, or initiation of any rectal corticosteroids during the Induction Study regardless of rectal corticosteroid dose;
- subjects on UC-related rectal corticosteroids at Baseline who have dosages increased to greater than the dose taken at Baseline, or initiation of any new type of rectal or any systemic corticosteroids during the Induction Study.

The time point of the UC-related corticosteroids intercurrent event is defined as the date when one of the scenarios above occurs for a subject. As such, subjects will be considered as "non-responder" for binary endpoints at or after the occurrence of the UC-related corticosteroids intercurrent event through the end of the Induction Study. For continuous endpoints, all measurements at or after the occurrence of the UC-related corticosteroids intercurrent event through the end of the Induction Study will not be used in the analysis.

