5.2.1 Inclusion Criteria

A subject will be eligible for study participation if he/she meets the following criteria:

1. Male or female ≥ 16 and ≤ 75 years of age at Baseline.
 - Adolescent subjects at the age of 16 and 17 years old will be enrolled if approved by the country or regulatory/health authority. If these approvals have not been granted, only subjects ≥ 18 years old will be enrolled
 - Adolescent subjects at the age of 16 and 17 years old must weigh ≥ 40 kg and meet the definition of Tanner Stage 5 (refer to Appendix H) at the screening Visit

2. Diagnosis of UC for 90 days or greater prior to Baseline, confirmed by colonoscopy during the Screening Period, with exclusion of current infection, colonic dysplasia and/or malignancy. Appropriate documentation of biopsy results consistent with the diagnosis of UC, in the assessment of the investigator, must be available.
3. Active UC with an Adapted Mayo Score of 5 to 9 points and endoscopy subscore of 2 to 3 (confirmed by central reader).
4. Demonstrated an inadequate response to, loss of response to, or intolerance to at least one of the following treatments including, oral aminosalicylates, corticosteroids, immunosuppressants, and/or biologic therapies, in the opinion of the investigator, as defined below:

Note: An inadequate response, loss of response, or intolerance to Oral Aminosalicylates will NOT count towards eligibility for the following countries: Austria, Czechia, Finland, France, Ireland, Italy, Latvia, Lithuania, Norway, Poland, Portugal, Spain, Sweden and United Kingdom.

- Oral aminosalicylates (e.g., mesalamine, sulfasalazine, olsalazine, balsalazide)
 - Signs and symptoms of persistently active disease, in the opinion of the investigator, during a current or prior course of at least 4 weeks of treatment with 2.4 g/day mesalamine, 4 g/day sulfasalazine, 1 g/day olsalazine, or 6.75 g/day balsalazide.
- Corticosteroids
 - Signs and symptoms of persistently active disease despite a history of at least one induction regimen that included a dose equivalent to prednisone ≥ 40 mg/day orally for at least 3 weeks or intravenously for 1 week, OR
 - Unable to taper corticosteroids to below a dose equivalent to prednisone 10 mg daily orally without recurrent active disease, OR
 - Signs and symptoms of persistently active disease during or after a course of at least 4 weeks of treatment with 9 mg/day budesonide or 5 mg/day beclomethasone, OR

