5.2.2 Exclusion Criteria

1. Subject with current diagnosis of Crohn's disease (CD) or diagnosis of indeterminate colitis (IC).
2. Current diagnosis of fulminant colitis and/or toxic megacolon.
3. Subject with disease limited to the rectum (ulcerative proctitis) during the screening endoscopy.
4. History of colectomy (total or subtotal), ileoanal pouch, Kock pouch, or ileostomy or is planning bowel surgery.
5. Received treatment with rectal aminosalicylates or corticosteroids, other enemas/suppositories (other than required for endoscopy), within 14 days prior to the Screening endoscopy and during the remainder of the Screening Period.

6. Received cyclosporine, tacrolimus, mycophenolate mofetil, or thalidomide within 30 days prior to Baseline.
7. Subjects who received azathioprine or 6-mercaptopurine within 10 days of Baseline.
8. Received intravenous corticosteroids within 14 days prior to Screening or during the Screening Period.
9. Subject on MTX or oral aminosalicylates who:
 - Has not been on the current course of MTX for at least 42 days prior to Baseline, and has not been on stable doses for at least 28 days prior to Baseline;
 - has not been on stable doses of oral aminosalicylates for at least 14 days prior to Baseline;
 - has discontinued use of aminosalicylates within 14 days of Baseline.
10. Subject on treatment with corticosteroids who meet the following:
 - Oral corticosteroid dose > 30 mg/day (prednisone or equivalent) or has not been on the current course for at least 14 days prior to baseline and on a stable dose for at least 7 days prior to Baseline;
 - Oral budesonide dose > 9 mg/day or has not been on the current course for at least 14 days prior to Baseline and on a stable dose for at least 7 days prior to Baseline
 - Oral beclomethasone dose > 5 mg/day; or has not been on the current course for at least 14 days prior to baseline and on a stable dose for at least 7 days prior to Baseline
 - Subject has been taking both oral budesonide (or oral beclomethasone) and oral prednisone (or equivalent) simultaneously, with the exception of topical or inhalers within 14 days prior to Screening or during the Screening Period.
11. Subject has active TB or meets TB exclusionary parameters (refer to Section 5.3.1.1 for specific requirements for TB).

12. Subject who received fecal microbial transplantation within 30 days prior to Baseline.

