- Intravenous corticosteroid use is prohibited within 14 days prior to Screening or during the Screening Period and during the study. (Initiating rectal or systemic corticosteroids use is prohibited during the induction treatment

period. Patients who initiate rectal or systemic corticosteroid for any reason during the study must be discussed with the TA MD.)

- Rectal aminosalicylates or corticosteroid enemas/suppositories are prohibited within 14 days prior to Screening endoscopy, during the remainder of the Screening Period, and during the study.
- Cyclosporine, tacrolimus, mycophenolate mofetil or thalidomide use is prohibited within 30 days prior to Baseline and during the study.
- Azathioprine or 6-mercaptopurine (6-MP) use is prohibited within 10 days prior to Baseline and during the study.
- NSAID (except topical NSAIDs and the use of low dose aspirin for cardiovascular protection) within 7 days prior to Baseline and during the study.
- Total parenteral nutrition is prohibited during the study.
- Cytapheresis treatment is prohibited within 60 days prior to Screening and during the study.
- Concomitant cannabis use, either recreational or for medical reasons, is prohibited at least 14 days prior to Baseline and during the study.
- Traditional Chinese medicines are prohibited within 30 days prior to Baseline and during the study.

Investigational Drugs

Investigational drugs of a chemical or biologic nature are prohibited within 30 days, or 5 half-lives (whichever is longer) of the drug prior to the Baseline and during the study.

Strong CYP3A Inhibitors or Inducers

Systemic use of strong CYP3A inhibitors or strong CYP3A inducers is prohibited from the Screening Visit through the end of the study. Examples of the most common strong CYP3A inhibitors and inducers are shown below:

Strong CYP3A Inhibitors	Strong CYP3A Inducers
Boceprevir Cobicistat Clarithromycin Conivaptan Grapefruit (juice or fruit) Indinavir Itraconazole Ketoconazole Lopinavir/Ritonavir Mibefradil Nefazodone Nelfinavir Posaconazole Ritonavir Saquinavir Telaprevir Telithromycin Troleandomycin Voriconazole	Avasimibe Carbamazepine Phenytoin Rifampin (Rifampicin) St. John's Wort

In Japan, the following therapies are also prohibited:

- ATM treatment (antibiotic combination therapy with amoxicillin, tetracycline and metronidazole) during the Screening Period and during the study.

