8.1.3 Definition of Missing Data Imputation

Missing data will be imputed using one or more of the following methods:

Non-Responder Imputation (NRI): In NRI analyses, subjects who prematurely discontinue the study prior to efficacy assessment at Week 8/Week 16 will be considered non-responders with respect to the efficacy endpoint.

Observed Cases (OC): The OC analysis will not impute values for missing evaluations, and thus a subject who does not have an evaluation on a scheduled visit will be excluded from the OC analysis for that visit.

Depending on the magnitude of missing data due to COVID-19, additional appropriate analysis of missing data may be performed with details included in the SAP.

The SFS and RBS at an assessment visit will be calculated as an average of the entries recorded into the subject's diary from the most recent consecutive 3-day period prior to each study visit. If diary entries from the 3 consecutive days prior to the visit are not available, the 3 most recent consecutive days in the last 10 days will be utilized. If data are not available for 3 consecutive days, the average of the entries from the most recent 3 non-consecutive days in the last 10 days will be utilized. If less than 3 days of diary data are available, SFS and RBS will be considered missing. Clinical endpoints of abdominal pain and bowel urgency from subject diaries will be measured at the same time period as the SFS and RBS.

Subjects in whom UC-related corticosteroids are initiated during treatment (not taken at Baseline) or who have dosages of these medications increased to greater than the dose taken at Baseline will be considered a failure for categorical efficacy endpoints and will have the last values carried forward for non-categorical assessments from that time point through the end of the study.

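### Does SAP 8.2.2 leave oral budesonide and beclomethasone outside the corticosteroid intercurrent event?

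*SAP*

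**What the plan says.** SAP 8.2.2 lists three situations that make up the event. The first is "subjects not on UC-related corticosteroids (systemic or locally acting corticosteroids for UC) at Baseline who initiated UC-related corticosteroids during the Induction Study". The second concerns "subjects on UC-related systemic corticosteroids at Baseline who have dosages increased to greater than the prednisone equivalent dose of corticosteroid taken at Baseline", and also counts any rectal start in those subjects. The third concerns "subjects on UC-related rectal corticosteroids at Baseline who have dosages increased to greater than the dose taken at Baseline", and also counts a new type of rectal steroid or any systemic start. From the event onward the subject is a non-responder for binary endpoints, and continuous measurements are not used.

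Protocol 8.1.3 has a shorter rule without drug classes. It begins "Subjects in whom UC-related corticosteroids are initiated during treatment (not taken at Baseline", adds doses raised above the Baseline dose, and counts both as failure for categorical endpoints.

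On entry, protocol 5.2.2 (criterion 10) sets separate limits for prednisone or equivalent, for budesonide (excluded if "Oral budesonide dose > 9 mg/day") and for beclomethasone (excluded if "Oral beclomethasone dose > 5 mg/day"). Stable use within those limits is allowed. Protocol 5.2.1 likewise names "9 mg/day budesonide or 5 mg/day beclomethasone" apart from the prednisone-equivalent criteria. Protocol 5.2.3.3 uses a two-way division: "Initiating rectal or systemic corticosteroids use is prohibited during the induction treatment" period.

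**The concern.** The first bullet of SAP 8.2.2 mentions systemic and locally acting steroids as two kinds. The bullets for subjects already on treatment mention only systemic and rectal. Oral budesonide and beclomethasone are allowed at Baseline and named in none of them. If they form a third, locally acting class, two groups meet no bullet: Baseline users of these drugs who raise the dose or start another steroid, and Baseline prednisone users who add one of them. Protocol 8.1.3 counts at least the dose increases as failures.

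The event decides non-response for the primary endpoint and the ranked binary endpoints under both NRI-C and NRI-NC, and which IBDQ and FACIT-F values are left out of the MMRM. Comparing NRI-C with NRI-NC would not reveal a problem, because both use the same flag. A subject who increased steroids could then count as a remitter, depending on a drug classification the SAP does not state. The version history in SAP 13.0 records no intended narrowing of the protocol rule.

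**Working it through.** **1. What each reading flags.** Subjects on no UC steroid at Baseline are covered on any reading, because the first bullet takes in every start. The question concerns only subjects already on a steroid.

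| Baseline | Change during induction | Oral agents treated as systemic | Oral agents treated as a separate class |
|---|---|---|---|
| Budesonide or beclomethasone | Same drug, dose raised | Flagged | Not flagged |
| Budesonide or beclomethasone | Prednisone added | Flagged | Not flagged |
| Budesonide or beclomethasone | Rectal steroid started | Flagged | Not flagged |
| Prednisone | Budesonide or beclomethasone added | Flagged | Not flagged |
| Either oral agent | Stopped and replaced by another oral agent | Depends on the conversion | Not flagged |
| Rectal | Budesonide or beclomethasone started | Flagged | Not flagged |

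In the systemic column, rows 1, 2 and 4 need no conversion table. If the conversion factor is any positive number, a higher dose of the same drug, or a second drug added to an unchanged first, raises the prednisone-equivalent total. Only row 5 needs a figure. Row 6 should be nearly empty, because protocol 5.2.2 (criterion 5) excludes rectal steroids during Screening.

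**2. The plan's own figure.** SAP 2.4 assumes 5% remission on placebo (n = 154) and 18% on upadacitinib (n = 308), with a two-sided Fisher's exact test at 0.05, and states power above 95%. Full enumeration of both binomials gives 98.9%, so the statement is reproduced.

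**3. Size on the less favourable reading.** The documents give neither the share of subjects on these drugs at Baseline nor the rate of steroid starts. The following are assumptions:

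- share s on oral budesonide or beclomethasone: 5% or 10% (23 to 46 of 462)
- start or increase during induction: 5% or 20% of those on placebo, 2% or 10% of those on upadacitinib
- Week 8 remission among them: 5% or 18%, set separately in each arm

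Expected false remitters in an arm = n × s × start rate × remission rate. All 2^5 = 32 combinations were run, adding the false remitters to the planned 5% and 18%.

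- Smallest difference (s 10%, starts 20% and 2%, remission 18% and 5%): placebo 154 × 0.10 × 0.20 × 0.18 = 0.554; upadacitinib 308 × 0.10 × 0.02 × 0.05 = 0.031. Rates 5.36% and 18.01%, difference 12.65 points, power 98.3%.
- Largest difference (s 10%, starts 5% and 10%, remission 5% and 18%): placebo 154 × 0.10 × 0.05 × 0.05 = 0.039; upadacitinib 308 × 0.10 × 0.10 × 0.18 = 0.554. Difference 13.16 points (13.155 unrounded), power 99.0%.
- Total false remitters over all 32: 0.03 to 1.1. The difference is below 13 points in 22 combinations and above it in 10.

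Baseline prednisone users who add one of these drugs are not in this count. Each further misclassified subject moves the placebo rate by 1/154 = 0.65 points or the upadacitinib rate by 1/308 = 0.32 points.

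**4. A harsher check.** Suppose 2% of an arm were false remitters, about 3 on placebo or 6 on upadacitinib. In both arms equally, the difference stays at 13 points and power is 97.3%. In the placebo arm alone, it is 11 points and 92.0%. In the upadacitinib arm alone, it is 15 points and 99.8%. The placebo-only case needs about 3.1 / 0.554 = 5.6 times the largest placebo count in the grid.

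**The case for a change.** The best case for changing the plan rests on pre-specification. The rule decides who is a responder, it should be settled before the sponsor is unblinded at database lock, and stating a class would cost a sentence. The systemic reading does not close everything either, since a change from one oral agent to another needs an equivalence that neither document supplies. SAP 8.3.1 also says that NRI-NC is the protocol's NRI, which would not be exact if the steroid rule had narrowed.

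Part of this stands. The class and the conversion are unstated, and replacement of one oral agent by another is unresolved.

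The rest is weaker. A separate oral locally acting class appears in neither document, and it would leave an admitted Baseline group with no rule at all. Treating locally acting as rectal makes the three bullets exhaustive and agrees with protocol 5.2.3.3. Protocol 8.1.3 gives no conversion and can be read by drug or by category; on the category reading, a straight switch is not clearly an initiation. Its NRI definition and its steroid rule are separate paragraphs, so the statement about NRI-NC can fairly be taken to describe missing-data handling only. Protocol 8.1 leaves full analysis detail to the SAP, and a conversion list is ordinary programming-specification material.

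Exposure is also limited. Protocol 5.2.3.2 asks for stable doses of UC-related medication, and 5.2.3.3 prohibits new rectal or systemic steroids during induction. SAP Appendix A tabulates prohibited medication, and SAP 8.4.4 repeats the primary analysis without subjects whose deviations could affect it. These provisions do not define the class, but they limit how often it matters.

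A new three-class rule could also change results. If any start in a new class were an event, replacing prednisone by budesonide at a lower equivalent dose would become a failure; simply calling the oral agents systemic would not make it one.

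**Conclusion.** The text has a gap that analysts would fill sensibly, and no change to the plan is needed. Oral budesonide and beclomethasone fit the systemic bullet of SAP 8.2.2. Dose increases, add-ons and rectal starts are then caught, and only replacement of one oral agent by another depends on a conversion the SAP does not give. That residue should be smaller than the range computed for the less favourable reading: at most about 1.1 expected misclassified subjects among 462, a difference of 12.65 to 13.16 points against 13 planned, and power of 98.3% to 99.0%. Those figures rest on the assumed rates of use, starts and remission, and leave out prednisone users who add one of these drugs. The direction is undetermined. Under these assumptions the primary conclusion does not depend on how the gap is filled.

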#### 8.3 Handling of Missing Data

Missing data could occur due to various reasons, including missing visits/assessments, early withdrawal from the Induction Study, or missing due to COVID-19 infection or logistical restrictions.

The COVID-19 pandemic is interfering with the conduct of many ongoing trials, with potential impacts on treatment duration and the collection, analysis and the interpretation of clinical trial data. Some protocol-specified visits in the clinical trials may be impacted due to COVID-19 infection or logistical restrictions during the pandemic. For example, some scheduled visits may be missed due to self-quarantine or local government restrictions on travel; some visits may also be delayed or canceled due to healthcare resource constraints during the pandemic. Impacted visits due to COVID-19 will be recorded in the database. The probability of having missed visits and missing data due to COVID-19 infection or logistical restrictions related to the COVID-19 pandemic can be reasonably assumed to be unrelated to the unobserved values. Therefore, for the purpose of statistical analysis, it is reasonable to assume that these missing data are missing at random (MAR) and the statistical models that require MAR assumption are appropriate. The intent is to provide reliable estimates of the treatment effects under the scenario without the impact of COVID-19 pandemic.

[figure not shown]
Handling of missing data for the efficacy analyses is described below.

#### 8.3.1 Categorical Endpoints

For binary efficacy endpoints, missing data will be handled using the following approaches:

[figure not shown]
• The primary approach for handling missing data in the analysis of binary endpoints will use Non-Responder Imputation while incorporating Multiple Imputation (MI) to handle missing data due to COVID-19 (NRI-C).

The NRI-C will categorize any subject who does not have an evaluation during a pre-specified visit window (either due to missing assessment or due to early withdrawal from the study) as a non-responder for the visit. The only exception is that missing data due to COVID-19 infection or logistical restrictions related to the COVID-19 pandemic will be handled by Multiple Imputation (MI). At each visit, subjects will be characterized as responders or non-responders based on MI imputed values if missing due to COVID-19; otherwise, subjects will be considered as non-responders for missing due to

other reasons in the NRI-C approach. In addition, at or after the occurrence of the UC-related corticosteroids intercurrent event (see Section 8.2.2), subjects will be counted as non-responders.

- A sensitivity analysis for categorical endpoints will use NRI with No special data handling for missing due to COVID-19 (NRI-NC).
   NRI-NC will be performed in the same way as NRI-C without the exception above. Missing due to COVID-19 infection or logistical restrictions will also be counted as non-responders. Subjects at or after the occurrence of the UC-related corticosteroids intercurrent event will still be counted as non-responders. This is the same method as the "NRI" defined in the protocol.
- Hybrid Multiple Imputation Method (HMI): Sensitivity analysis will be performed using hybrid multiple imputation method for the primary endpoint. Subjects who discontinue study drug prior to Week 8 due to lack of efficacy or AEs and have no available measurements will be considered as "non-responder" for clinical remission. Subjects who discontinue for other reasons and have no available measurements will be categorized according to the data from multiple imputations.
- Multiple Imputation (MI) for NRI-C and HMI: Markov Chain Monte Carlo (MCMC) will be first applied to augment data into monotonic missing pattern, where applicable, and PROC MI will be used to generate 30 datasets using the regression method. The variables to be included in the imputation model are: treatment group, stratification factors (bio-IR status (bio-IR vs. non-bio-IR), Baseline corticosteroid use (yes vs. no) and Baseline Adapted Mayo score ( $\leq 7$ vs. > 7)), Baseline measurement, and if applicable, post-baseline measurements at each visit up to the end of the analysis period. The random seed for MCMC and the random seed for PROC MI are specified in Appendix D. The imputed post-baseline measurements will be rounded to the same precision as the observed data before the determination of responder status. Subjects will be characterized as responders or non-responders based on MI imputed datasets. Using the CMH model adjusted by stratification factors (bio-IR status (bio-IR vs. non-bio-IR), Baseline corticosteroid use (yes vs. no) and Baseline Adapted Mayo score ( $\leq 7 \text{ vs.} > 7$ ), the imputed endpoints will be analyzed using each of the 30 datasets. SAS PROC MIANALYZE will be used to generate the final treatment difference between upadacitinib

treatment group and placebo group and statistical inferences of the risk difference, including hypothesis testing, and 95% CI using Rubin's rule and T-distribution. Note that measurements will be set as missing at or after the occurrence of the UC-related corticosteroids intercurrent event before applying MI. After the MI imputation, an NRI override will be implemented for missing values 1) due to reasons other than COVID-19 infection or logistic reasons, or 2) at or after the occurrence of the UC-related corticosteroids intercurrent event, that is, regardless of MI imputed values, subjects satisfying 1) or 2) will be considered as "non-responder" for binary efficacy.

 As Observed (AO): The AO analysis will not impute values for missing evaluations, and thus a subject who does not have an evaluation on a scheduled visit will be excluded from the AO analysis for that visit. AO will include all values collected in the study.

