We propose to initiate a Phase 3 study in UC subjects based on the following supportive findings: 1) demonstrated improved potency of upadacitinib versus tofacitinib in preclinical models of inflammation; 2) confirmed JAK1 selectivity of upadacitinib in both preclinical and clinical settings; 3) acceptable preclinical toxicological findings in chronic toxicity studies in two species; 4) acceptable safety and tolerability profile of upadacitinib in single ascending dose and multiple ascending dose studies in healthy volunteers; 5) evidence that JAK inhibition in inflammatory bowel disease results in clinical and endoscopic improvement; and 6) evidence of efficacy and safety in a different inflammatory disease (rheumatoid arthritis). The current Phase 3 Study M14-675 will assess the benefit to risk profile of upadacitinib in subjects with moderately to severely active UC who have had an inadequate response or intolerance to oral aminosalicylates, immunosuppressants, corticosteroids, and/or biologic therapies.

As presented above, the completed Phase 2 dose ranging Study M14-234 Substudy 1 has demonstrated superior efficacy of upadacitinib with an acceptable safety profile compared to placebo in subjects with moderately to severely active UC. The benefit-risk profile of upadacitinib in this Phase 2 study supports further evaluation of upadacitinib in subjects with UC.²⁴

In view of the coronavirus (COVID-19) pandemic, the benefit:risk profile of various immunomodulatory therapies on COVID-19 is being evaluated. At this time, the effects of upadacitinib on the course of COVID-19 are not well defined.

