Refer to the Section 5.3.1.1 and [Appendix C](#) for details on how to handle study activities/procedures.

Interruption/Discontinuation of Study Drug Due to COVID-19 Infection

For subjects with signs and/or symptoms and suspicion of COVID-19 or if a diagnosis has been confirmed, study drug should not be administered until the infection has resolved or coronavirus infection has been ruled out. There are no time limits for study drug interruption as long as no permanent study discontinuation criteria have been met. The PI should contact the TA MD before reintroducing study drug in subjects who were infected with COVID-19. The study drug interruption should be captured on related CRFs with reasons due to COVID-19.

For subjects who are asymptomatic and had primary exposure to COVID-19 (e.g., family member tests positive) or have concerns about taking upadacitinib with ongoing COVID-19 transmission. The investigator can decide to continue or interrupt study drug on a case-by-case basis taking into account the risk:benefit of continuing study drug. The investigator can temporarily interrupt study drug at any time for a safety issue, or for any reason if they feel that the risk outweighs the benefit of study treatment.

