#### 2.4 Sample Size Determination

For Part 1, approximately 462 subjects are expected to be randomized to upadacitinib 45 mg QD or placebo in a randomization ratio of 2:1. The sample size for this study is based on the expected proportion of subjects who achieve clinical remission per Adapted Mayo score at Week 8. Based on the results from Phase 2b upadacitinib Study M14-234 (Substudy 1), the proportions of subjects achieving clinical remission per Adapted Mayo score in upadacitinib 45 mg QD group and placebo group are 19.6% and 0%, respectively. Considering the small sample size in Phase 2b study and more stringent definition of primary endpoint used for Phase 3 studies, clinical remission rate is assumed to be 5% in the placebo group and 18% in the upadacitinib 45 mg QD treatment group. Based on these assumptions, a sample size of 154 subjects in placebo and 308 subjects in upadacitinib dose will have > 95% power to detect the 13% treatment difference in the primary endpoint between upadacitinib 45 mg QD group and placebo group using two-sided Fisher's exact test at a 0.05 significant level.

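### NRI-C multiply imputes a COVID-missing Week 8 value even when the subject had already stopped study drug for lack of efficacy or a non-COVID adverse event, although HMI counts that subject as a non-responder

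*SAP*

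**What the plan says.** SAP 8.4.2 names NRI-C as the primary missing-data method for Week 8 clinical remission, with NRI-NC and HMI as sensitivity analyses. SAP 8.5.1 uses NRI-C for the binary ranked secondary endpoints too, with NRI-NC as the sensitivity analysis.

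Under NRI-C (SAP 8.3.1) a subject without an evaluation in the visit window is a non-responder, except: "The only exception is that missing data due to COVID-19 infection or logistical restrictions related to the COVID-19 pandemic will be handled by" multiple imputation. The paragraph on multiple imputation for NRI-C and HMI lists the model terms: "The variables to be included in the imputation model are: treatment group, stratification factors", then baseline and available post-baseline values. Whether the subject is still on drug is not among them. After imputation an override restores non-response in two situations: the value is missing for a non-COVID reason, or it falls at or after the UC-related corticosteroid event.

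HMI (same section) treats early stoppers differently: "Subjects who discontinue study drug prior to Week 8 due to lack of efficacy or AEs and have no available measurements will be considered" non-responders for remission. Those who stop for other reasons and have no measurement are multiply imputed. NRI-NC counts all COVID-missing values as non-response.

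SAP 8.2.1 uses collected data whether or not study drug was stopped. SAP 8.3 argues that COVID-related missingness is unrelated to the unseen value and says the aim is the effect as it would be without the pandemic.

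**The concern.** The NRI-C exception looks only at why the value is missing, not at what happened to the subject beforehand. Protocol 5.4.1 keeps subjects who stop drug in scheduled follow-up, so someone who stopped at Week 3 for lack of efficacy can later miss the Week 8 endoscopy because of the pandemic. The timing allows it: SAP Appendix D dates the last randomization to 26 May 2020, which puts the last nominal Week 8 visit 56 days later, on 21 July 2020.

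That subject would have been off drug at Week 8 with or without a pandemic. The imputation model will be fitted mostly to subjects still on drug, so the draw approximates an on-drug outcome for the subject's arm. This matches neither the no-pandemic scenario of SAP 8.3 nor an estimand defined whether or not drug was stopped. The same subject is also handled in opposite ways by the primary analysis and by HMI, with no rule for which reason takes precedence. At stake is a small distortion in the estimate of the primary endpoint and of every binary ranked secondary endpoint.

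**Working it through.** **1. The plan's own figure.** Inputs from SAP 2.4: "clinical remission rate is assumed to be 5% in the placebo group and 18% in the upadacitinib 45 mg QD treatment group"; "a sample size of 154 subjects in placebo and 308 subjects in upadacitinib dose will have > 95% power"; "using two-sided Fisher's exact test at a 0.05 significant level". Summing the binomial probabilities of all outcome pairs (154 at 0.05, 308 at 0.18) for which Fisher's two-sided p ≤ 0.05 gives power of 98.9%. The pooled normal approximation gives 98.8%. The stated > 95% is reproduced.

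**2. Classify a missing Week 8 value (no corticosteroid event).**

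| Cell | Situation | NRI-C | HMI | NRI-NC |
|---|---|---|---|---|
| A | Stopped for adverse event or lack of efficacy; COVID-missing | imputed | non-response | non-response |
| B | Stopped for adverse event or lack of efficacy; missing for another reason | non-response | non-response | non-response |
| C | Stopped for other reasons; not COVID-missing | non-response | imputed | non-response |
| D | Stopped for other reasons; COVID-missing | imputed | imputed | non-response |

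NRI-C is more lenient than HMI in A and stricter in C.

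**3. Size per subject in cell A.** The documents give no count for any cell. Take the planning rate of the arm as the chance that an imputed value is a remission:

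- upadacitinib: 100 × 0.18 / 308 = 0.058 points, raising the difference;
- placebo: 100 × 0.05 / 154 = 0.032 points, lowering it.

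If every draw in an upadacitinib subject were a remission, the ceiling would be 100 / 308 = 0.32 points.

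**4. Assumed counts (upadacitinib/placebo).** Net shift = 100 × (u × 0.18/308 − p × 0.05/154). The last column is Fisher power if these subjects are made non-responders, against 98.9% if they are not.

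| u/p | Shift in difference from imputing | Power with non-response |
|---|---|---|
| 2/1 | +0.08 | 98.8% |
| 6/3 | 0.35 − 0.10 = +0.25 | 98.7% |
| 10/5 | +0.42 | 98.6% |
| 10/0 | +0.58 | 98.3% |
| 0/3 | −0.10 | not computed |

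The sign changes when placebo cases exceed 0.058 / 0.032 = 1.8 times upadacitinib cases.

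**5. Is NRI-C more lenient than HMI overall?** Assume equal cell shares in both arms, B = 2%, D = 3%, and imputation at the planning rates. In points the difference is then 13 × (1 − B − C) for NRI-C, 13 × (1 − A − B) for HMI, 13 × (1 − A − B − C − D) for NRI-NC, and 13 × (1 − A − B − C) for NRI-C with cell A set to non-response.

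| A | C | NRI-C | HMI | NRI-NC | NRI-C, A as non-response |
|---|---|---|---|---|---|
| 1% | 0% | 12.74 | 12.61 | 12.22 | 12.61 |
| 1% | 1% | 12.61 | 12.61 | 12.09 | 12.48 |
| 1% | 3% | 12.35 | 12.61 | 11.83 | 12.22 |
| 0.5% | 5% | 12.09 | 12.67 | 11.63 | 12.02 |

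Under these assumptions NRI-C exceeds HMI only when A exceeds C. NRI-NC is lowest in every row.

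**6. A conflict within SAP 8.3.1.** The override stands in the paragraph headed for both NRI-C and HMI. Read literally, it turns cell C into non-response under HMI as well, cancelling the imputation that the HMI bullet prescribes. HMI could then never be more lenient than NRI-C. The two passages need reconciling.

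**The case against.** The strongest reply is that the plan already brackets the problem. NRI-NC sets every COVID-missing value to non-response for the primary and binary secondary endpoints. This stands as a bound. It does not isolate the overlap, because it also removes imputation for subjects who were on drug and merely missed a visit.

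Second, imputation draws Mayo subscores using earlier values, so it does not hand out remission. Stool frequency and rectal bleeding come from a home diary and may be observed when only the endoscopy is missed; a subject who stopped for lack of efficacy will often fail on those alone. Subjects who start or escalate UC-related corticosteroids are already non-responders. All of this stands and makes 0.06 points per upadacitinib subject more likely too high than too low.

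Third, non-response is itself an assumption and is not by definition closer to an estimand that disregards stopping drug. That is fair. The argument for it here is consistency: NRI-C applies it to every other missing value, and HMI applies it to these subjects.

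Fourth, COVID-19 infection may look like the clearest case, since Protocol 6.1.5 records it as an adverse event and Protocol 3.2 says "the effects of upadacitinib on the course of COVID-19 are not well defined". But imputing infection-related missingness is the declared intent of SAP 8.3. The documents do not say how such a stop would be coded for HMI. The Protocol 5.4.1 statement "There are no time limits for study drug interruption as long as no permanent study discontinuation criteria have been met" concerns temporary interruption, not permanent stopping. Imputation after a stop due only to infection is therefore a disclosed trade-off, not a defect.

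**Conclusion.** The point holds in a narrow form. For subjects who permanently stopped study drug for lack of efficacy or a non-COVID adverse event and whose Week 8 value is COVID-missing, the primary rule imputes without using off-drug status, HMI assigns non-response, and the SAP gives no precedence. Neither SAP 8.2 nor 8.3 says how a death before Week 8 is handled for efficacy.

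A reader might infer that the primary analysis is more lenient than HMI as a whole, or that the bias always favours upadacitinib. The documents support neither. HMI imputes other-reason stoppers whom NRI-C fails, so the order depends on unknown cell sizes unless the override is read as governing HMI too. The direction depends on unknown counts by arm, and more lack-of-efficacy stops on placebo could narrow or reverse it.

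The size is small: about 0.25 points for an assumed 6 and 3 subjects, with power staying between 98.3% and 98.8% in the scenarios computed. These figures rest on the planning rates, assumed counts, and imputation reproducing each arm's planning rate. The trial's conclusion is not threatened; this is a cheap improvement to the primary estimator.

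**What to change.** In the multiple-imputation paragraph of SAP 8.3.1, add a third override condition: a missing value is non-response if, before the missed assessment, the subject had permanently stopped study drug for lack of efficacy or for an adverse event other than COVID-19 infection, or had died. Say whether the primary reason or any recorded reason counts, since SAP 5.0 summarizes both. Keep multiple imputation for all other COVID-missing values, including after stops due only to COVID-19 infection, in line with SAP 8.3; NRI-NC covers the strict alternative.

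Report the number of subjects meeting the new condition by arm. State whether the override applies to HMI; if HMI is meant to impute other-reason stoppers, limit that part of the override to NRI-C.

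The cost is a few sentences in the SAP and one condition in the program. The last dose date and discontinuation reason (Protocol 5.4.1), date of death (Protocol 6.1.1.2) and COVID-impacted visits (SAP 8.3) are already recorded. The downside is that remission rates may be marginally lower.
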